**Summary:**

ECG measurements will be summarized by treatment and study day, for each dose schedule separately and across dose schedule.

- ECG measurements will be summarized as follows:
  - The frequency distribution of subjects’ maximum recorded post-dose QTcF, PR, QRS,  $\Delta$ QTcF will be summarized and tabulated for the following ranges:
    - ◆ For QTcF:  $QTcF \leq 450$  msec,  $450 \text{ msec} < QTcF \leq 480$  msec,  $480 \text{ msec} < QTcF \leq 500$  msec,  $QTcF > 500$  msec
    - ◆ For PR:  $PR \leq 200$  msec,  $PR > 200$  msec
    - ◆ For QRS:  $QRS \leq 120$  msec,  $QRS > 120$  msec
    - ◆ For  $\Delta$ QTcF:  $\Delta$ QTcF  $\leq 30$  msec,  $30 \text{ msec} < \Delta$ QTcF  $\leq 60$  msec,  $\Delta$ QTcF  $> 60$  msec
  - The frequency distribution of subjects’ maximum recorded post-dose HR and  $\Delta$ HR and of minimum recorded post-dose HR and  $\Delta$ HR will be summarized and tabulated for the following ranges:
    - ◆ HR and  $\Delta$ HR: HR Value  $> 100$  bpm with  $\Delta$ HR  $> 30$  bpm or
    - ◆ HR value  $< 55$  bpm with  $\Delta$ HR  $< -15$  bpm
  - Summary statistics (n, mean, standard deviation, median, minimum, and maximum) will be presented for each ECG parameter and the corresponding changes from baseline by treatment and time point.
  - Linear mixed effects regression model of  $\Delta$ QTcF vs. BMS-986158 will be provided across dose schedules at Cycle 1 Day 1 (single dose), and may also be provided separately by dose schedule at steady state. The same model will be repeated on the active metabolite plasma concentrations if the latter is sufficiently measured
    - ◆ The plot of  $\Delta$ QTcF versus drug concentrations will include the estimated linear regression taken from the results of fitting a mixed effect model, if available. Mixed effect model with random intercept and slope will be used to explore the relationship between the  $\Delta$ QTcF and plasma concentration data. The following SAS® code is recommended.

```
proc mixed data=Data Set Name method=reml;  
  class usubjid;  
  model  $\Delta$ QTcF =concentration/solution cl alpha=0.10 ddfm=kenwardroger;  
  random intercept concentration/subject=usubjid type=un;
```
    - ◆ Use of option “empirical” will provide more robust estimate; Start with “type=un”, and then examine the covariance structure and adjust to reduce the number of parameters to be estimated, as needed. If, however, the SAS log file contains the “Note: Estimated G matrix is not positive definite.”, then the variances of the random intercepts or slopes may be so small that one or both should be replaced by fixed effects, i.e., dropped from

the random statement. The point estimate and 90% confidence interval for the slope will be reported within the CSR text

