1.4.4.1 Pharmacokinetics of BMS-986158

BMS-986158

Interim noncompartmental PK analyses were conducted on BMS-986158 (parent) and BMT-161485 (metabolite) using samples from the monotherapy portion of the study administration of 0.75, 1.25, 2, 3, and 4.5 mg oral doses of BMS-986158 following single and multiple doses using nominal time and examining continuous and intermittent schedules (Schedules A and C, respectively).

Interim PK results indicate that BMS-986158 is moderately to rapidly absorbed (Tmax range: 0.5 to 4 hours) following single dose administration at doses of 0.75 to 4.5 mg. The exposure within the dose range examined appears to increase with increasing dose. From these multiple dosing data, a peak to trough ratio of approximately 2.4 and an accumulation index of approximately 1.97 were determined. The inter- and intra-subject variability was from low to high.

PK parameters of BMS-986158 using nominal sample times show that the overall exposure was significantly higher than predicted. This higher than predicted human exposure may have resulted from, and is consistent with a lower than anticipated clearance and increased serum protein binding in humans. Preclinical determinations of human serum protein binding indicated a 3.9% free fraction for BMS-986158. Interim data from ex vivo plasma samples collected from the 6 subjects at the 2 mg dose on this study showed mean free drug fractions of 0.1% to 0.2% with small to moderate intra- and inter-subject variability that were not concentration dependent. It is postulated that the unexpectedly low free fraction resulted in the low clearance.

The metabolite (BMT-161485) exhibited a similar terminal phase elimination as the parent drug, suggesting formation rate limited PK of BMT-161485. Plasma concentrations of metabolite were low relative to the plasma concentration of the parent drug with exposure ratios less than 30%. The metabolite has potency that is approximately 10-fold weaker than the parent drug.

Preclinical data suggests that BMS-986158 is metabolized in the liver by CYP3A4 mediated oxidation to a hydroxylated metabolite; it also undergoes glucuronidation. BMS-986158 is a substrate of CYP3A4 and an inhibitor of P-gp and transporters.

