8.4.5 ECG Analyses

For subjects with serial ECG measurements and time-matched PK following monotherapy treatment with BMS-986158, changes in the QTcF (Δ QTcF), ECG intervals QRS, and PR, and in heart rate (Δ HR) will be tabulated by treatment and study day. Frequency distributions of max QTcF values, max Δ QTcF, and of max HR in pre-specified categories will be tabulated by treatment. Scatter plots of heart rate, Δ HR, QTc, and Δ QTcF, vs time-matched BMS-986158 concentrations will be provided. A concentration-response effect of BMS-986158 on QTcF may be assessed by a linear mixed effects regression model for Δ QTcF on plasma and serum concentrations, stratified by study day, as well as pooled across days.

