During the dose expansion part of this study, BMS-986158 will initially be tested in subjects with TNBC, CRPC, DHL, non-GC-DLBCL, and NMC. These cancers are rare in children. Some predictors of poor outcome were shared among all age groups, such as multiple primary tumor sites and advanced stage disease. Because patient numbers are low, there are no randomized trials comparing different relapse regimens. These results provide rationale for development of alternative treatment approaches focusing on targeted therapy to circumvent chemotherapy-resistant disease by providing alternative therapeutic targets across different ages.

Current experience with BMS-986158 did not identify drug-related adverse events (AEs) that warrant exclusion of adolescent subjects from this study. Thus, the balance of benefit to risk may be favorable in adolescent subjects with advanced cancers and poor treatment options. Therefore, adolescent subjects with NMC will be eligible to participate in this study. Additional indications will be allowed at the discretion of the Sponsor if the tumor contains similar genetic abnormalities sensitive to regulation by the BET family proteins.

This SAP supersedes the statistical considerations identified in the protocol; where considerations are substantially different, they will be identified as such in this document. In the event that the protocol has amendment(s) that do not have an impact on the statistical analysis methodology, this SAP will not require an amendment. [REDACTED]

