**Figure:**

- ECG measures
  - Scatter plot and regression of  $\Delta$ QTcF on BMS-986158 concentration (with fitted line) on each study day. Scatter plots of QTcF, HR,  $\Delta$ HR on BMS-986158 concentration on each study day.

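### SAP 7.9 guarantees the concentration-QTcF mixed model only for the single dose on Cycle 1 Day 1, and omits the protocol's optional pooled-across-days model without saying so

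*SAP*

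**What the plan says.** Exposure-response on the QT interval is a secondary objective in both documents (Protocol 1.3.2, SAP 3.2).

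- **Protocol 8.4.5** makes the model optional: "A concentration-response effect of BMS-986158 on QTcF may be assessed by a linear mixed effects regression model". It describes that model as "stratified by study day, as well as pooled across days". The synopsis says the same in substance.
- **SAP 7.9, Summary list**: the model "will be provided across dose schedules at Cycle 1 Day 1 (single dose), and may also be provided separately by dose schedule at steady state". Its suggested code has a random intercept and slope per subject ("random intercept concentration/subject=usubjid type=un"). It ends: "The point estimate and 90% confidence interval for the slope will be reported within the CSR text".
- **SAP 7.9, Figure list**: a scatter plot and regression of change in QTcF "on BMS-986158 concentration (with fitted line) on each study day", with no *may*. The Summary list takes the plotted line from the mixed model if that model is available.
- **SAP Section 1** says of departures from the protocol that "where considerations are substantially different, they will be identified as such in this document". The SAP explains other changes, such as replacing TAU by 24 hours (4.2.2) and counting unconfirmed responses (4.2.1). It does not mention the missing pooled fit.
- **Protocol 1.4.4.1** reports that, from multiple-dose data, "an accumulation index of approximately 1.97 were determined".

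**The concern.** The one slope certain to reach the study report comes from the day with the lowest exposure. Using it to describe QT effect under repeated dosing means extrapolating beyond typical Day 1 concentrations, with a wider interval than necessary.

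The data that would fill the gap are already scheduled. If the optional steady-state fit is done, splitting it by schedule leaves very few subjects in Schedule B for an unstructured random intercept-and-slope model. The SAP itself anticipates a covariance matrix that is not positive definite. Whether a Cycle 2 mixed model will exist at all depends on which list in 7.9 is followed.

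**Working it through.** **Inputs from the documents.** Accumulation index (AI) 1.97 (Protocol 1.4.4.1; interim, exposure measure not named, underlying AUCs not given, so it cannot be reproduced). Half-life 39 h (Protocol 1.1.5). Part 1 subjects at the 21-Dec-2018 cutoff: Schedule A 44, B 8, C 29, total 81 (Protocol 1.4.4). ECG and PK times from Protocol Tables 5.5.1-1 to 5.5.1-3. Part 2 regimen: 4.5 mg for 10 doses, then 3.75 mg (Protocol 3.1). The documents give no precision target for the QT slope.

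**1. Exposure on Day 1 against repeat dosing.**
- Same dose: 1/1.97 = 0.51.
- Loading period: repeat-dose 4.5 mg against a single 4.5 mg dose = 1.97.
- Continuing dose: 3.75 × 1.97 / 4.5 = 1.64.
- Cross-check from the half-life: r = exp(−ln 2 × 24/39) = 0.653. AI at the fifth daily dose = (1 − r⁵)/(1 − r) = 2.54; at steady state 1/(1 − r) = 2.88. The Day 1 share would then be 0.39 to 0.35, so one half is, if anything, generous.
- By the SAP's own formula, AI 1.97 corresponds to an effective half-life of 24 × ln 2 / ln(1.97/0.97) = 23.5 h. The gap from 39 h is effective against terminal half-life, not an error.

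**2. Time-matched post-dose records per subject, as scheduled.**
- Cycle 1, all schedules: 2, 4, 8 and 24 h = 4.
- Cycle 2, A: Days 1, 2, 5 (predose, 2, 4, 8 h), 6 and 8 = 8. B: Day 14 (four times) and Day 15 = 5. C: Day 7 (four times) and Days 8 to 11 = 8.
- Cycle 1 only: 81 × 4 = 324 (243 without the 24 h sample). Both cycles: 44 × 12 + 8 × 9 + 29 × 12 = 528 + 72 + 348 = 948.

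**3. Standard error of the slope.** Generalised least squares information, the sum over subjects of X′V⁻¹X, for the SAP's model form at the doses given. Assumed, because the documents are silent: one-compartment PK with absorption rate 1.2/h; half-life 23.5 or 39 h; PK CV 0 to 60%; residual SD 6 to 8 msec; intercept SD 6 to 10 msec; slope SD 0 to 0.04 msec per ng/mL; day SD 0 to 8 msec; all 81 subjects evaluable. Later cycles and Part 2 are left out.

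| Pooled model | Day 1 SE ÷ pooled SE |
|---|---|
| No fixed day factor, 24 h sample counted with Day 1 | about 1.8 to 6 |
| Same, 24 h sample left out of Day 1 | up to 6.7 |
| Study day as a fixed factor, with noisier single ECGs in Cycle 2 | about 1.4 to 4 |

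The last row is closest to the model recommended here. Its lower end comes with a large random slope or a much larger Cycle 2 residual SD.

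**4. One worked case.** Half-life 23.5 h, intercept SD 6, slope SD 0.01, day SD 5 (random), residual SD 8, no PK variability: SE 0.0075 (Day 1) against 0.0024 (pooled) msec per ng/mL. At the top modelled Cycle 2 concentration of 786 ng/mL, the slope's 90% half-width is 1.645 × 0.0075 × 786 = 9.7 msec against 1.645 × 0.0024 × 786 = 3.1 msec (3.2 before rounding the SE).

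**The case against.** The best defence has four parts.

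1. A reader might infer that the SAP confines QT modelling to Day 1 and sets Cycle 2 aside. It does not: the Figure list plans a regression on each study day and the Summary list permits a steady-state model. Section 7.9 also firmly requires change in QTcF by treatment and time point, and categories of each subject's maximum post-dose QTcF and change. This stands. What remains is that these are separate fits or descriptive tables, and the Summary list leaves the steady-state mixed model optional.
2. A reader might infer a broken protocol commitment. The protocol model was itself optional, and the SAP made the single-dose fit firm. This stands too. The omission narrows an optional analysis, and whether it is substantial enough to trigger the SAP's flagging promise is arguable.
3. A reader might take treatment exposure to be twice anything seen on Day 1. At 3.75 mg the mean ratio is about 1.6, because Day 1 includes 23 subjects given 4.5 mg (12 in A, 11 in C), and individual concentrations overlap.
4. Day 1 has triplicate ECGs at predose, 2 h and 4 h, with single ECGs afterwards, and pooling assumes a common slope across days. Both points reduce the gain; neither reversed it in the scenarios tried.

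**Conclusion.** The concern holds as a gap in commitment and clarity on a secondary objective. The guaranteed mixed model uses about half the repeat-dose exposure at the same dose. The steady-state model is optional and split by schedule, the pooled model has gone without comment, and the two lists in 7.9 disagree.

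The Day 1 slope is less precise than the scheduled data allow, by a factor of roughly 1.4 to 6.7 in standard error, or about 1.4 to 4 once study day is a factor and single ECGs are allowed for. The size rests on assumed variance components and PK, so no single multiplier should be quoted. The direction was the same in every scenario. Some extrapolation is needed: about 1.6 times in mean exposure at 3.75 mg and about 2 times during loading, taking the stated AI and dose-proportional exposure.

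**What to change.** In SAP 7.9:

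- Commit to one mixed model over all scheduled Part 1 serial ECG/PK days and all three schedules, with study day as a factor and a residual variance that differs between averaged triplicate and single ECGs.
- Report its slope, and the predicted change in QTcF with 90% CI at the geometric-mean steady-state Cmax for the Part 2 regimen. The 3.75 mg dose is not among the Part 1 doses listed at the cutoff, so say where its Cmax will come from.
- Keep the Day 1 and by-day fits as supportive, and use the by-day fits to check the common-slope assumption.
- Make the Summary and Figure lists agree on whether Cycle 2 fits are planned or optional.
- If the sponsor prefers not to pool, state that this departs from Protocol 8.4.5 and why.

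The cost is SAP wording and one more model run. No new data are needed.

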## **7.9 Electrocardiogram (ECG)**

All of the available ECG parameter values, single and triplicates, from each participant will be included in the ECG data set. Although all recorded ECG parameter values will be included in the data listings, only ECG parameters with scheduled visits will be included in the summary statistics, graphs, and statistical analysis. Only Part 1 participants will be summarized unless there are more than 5 participants in Part 2.

The triplicate measurements will be averaged at each scheduled measurement timepoints. Baseline values are defined as the average of last recorded triplicate values prior to the first dosing. If triplicate values are not the last recorded values prior to the first dosing, the last recorded value

prior to the first dosing will be used as baseline. For ECG parameters such as QTcF, QT, QTcB, heart rate (HR), QRS, and PR, summary measures (n, mean, standard deviation, median, minimum, and maximum) will be provided.

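### The concentration-QTc model has no term for time after dose, so part of any common within-day QTcF change enters the reported slope, in either direction

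*SAP*

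**What the plan says.** The exposure-response effect on the QT interval is a secondary objective (SAP 3.2; Protocol 1.3.2). For it, SAP 7.9 says: "Mixed effect model with random intercept and slope will be used to explore the relationship between the" change in QTcF and concentration. The only fixed effect in the MODEL statement is concentration ("concentration/solution cl alpha=0.10 ddfm=kenwardroger"), and the subject terms are "random intercept concentration/subject=usubjid type=un".

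The regression "will be provided across dose schedules at Cycle 1 Day 1 (single dose"); a steady-state fit by schedule is optional. The SAP introduces the SAS lines with the words "code is recommended". Its guidance on altering the model concerns the robust-variance option, the random terms and the covariance ("examine the covariance structure and adjust to reduce the number of parameters to be estimated, as needed"), not the fixed effects. On output: "The point estimate and 90% confidence interval for the slope will be reported within the CSR text".

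Baseline is well defined: "Baseline values are defined as the average of last recorded triplicate values prior to the first dosing". It is used only to form the change score. Time point appears only in the descriptive tables. Protocol 8.4.5 would stratify by study day or pool days, which does not address time within a day.

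**The concern.** In Part 1 the first-cycle ECGs are taken predose and at 2, 4, 8 and 24 h after one dose (Protocol Tables 5.5.1-1 to 5.5.1-3). Interim Tmax is 0.5 to 4 h (Protocol 1.4.4.1), so concentration tends to be high at the early readings and lower at 24 h in most subjects. If QTcF also shifts over those hours for reasons unrelated to the drug, the two patterns overlap.

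Random subject intercepts and slopes do not remove a pattern that all subjects share, and there is no control group to subtract it. The slope and its interval are the figures carried into the study report for a stated objective, so a shift in them could be read as a QT signal or could conceal one.

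**Working it through.** **No stated figure to reproduce.** The documents give no slope, SD, power or QTc threshold for this analysis. The one numeric setting is consistent: alpha = 0.10 gives a two-sided 90% interval (multiplier 1.645).

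**Mechanism.** Write the change in QTcF for subject i at time t as m(t) + β·c_i(t) + error, where m(t) is drift common to all subjects. If m(t) is omitted, the part of it that tracks c_i(t) goes into the slope and the rest into the intercept. Overlap is incomplete: with a 39 h half-life and single-phase decline, concentration falls from 2 h to 24 h by 1 − 2^(−22/39) = 0.32. At any one time, doses span 0.75 to 4.5 mg (sixfold), so time and concentration can be separated without placebo.

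**Inputs from the documents.**
- Dose mix at the December 2018 cutoff (Protocol 1.4.4): Schedule A 5 + 4 + 13 + 10 + 12 = 44; Schedule B 4 + 4 = 8; Schedule C 6 + 12 + 11 = 29; total 81.
- Post-dose ECGs at 2, 4, 8 and 24 h.
- Half-life 39 h (Protocol 1.1.5).

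**Assumed inputs.**
- Drift from predose of ±5, ±5, ±3, 0 ms or ±3, ±3, ±2, 0 ms at the four times.
- Residual SD 7 ms, baseline measurement SD 5 ms, log-scale exposure SD 0.4.
- Concentration relative to 2 h either single-phase, 2^(−(t−2)/39), giving 1, 0.97, 0.90, 0.68; or with a distribution phase, 0.4·2^(−(t−2)/4) + 0.6·2^(−(t−2)/39), giving 1, 0.86, 0.68, 0.41.

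**Method.** REML fit with random intercept and slope, unstructured; post-dose rows; 100 runs per setting; normal-approximation intervals rather than Kenward-Roger. The effect is the slope times the typical 2 h concentration at 4.5 mg.

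True drug effect zero:

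| Decline | Drift at peak (ms) | Planned model, mean (ms) | Planned, CI excludes 0 | Time + baseline added, mean (ms) | Time + baseline added, coverage |
|---|---|---|---|---|---|
| Single-phase | 0 | 0.1 | 16% | 0.2 | 84% |
| Single-phase | +5 | 3.3 | 55% | 0.0 | 85% |
| Single-phase | −5 | −3.2 | 59% | 0.3 | 89% |
| Single-phase | +3 | 1.8 | 24% | −0.4 | 86% |
| Single-phase | −3 | −2.0 | 36% | 0.1 | 89% |
| Distribution phase | 0 | 0.2 | 11% | 0.3 | 91% |
| Distribution phase | +5 | 5.3 | 94% | −0.2 | 83% |
| Distribution phase | −5 | −5.1 | 95% | 0.2 | 92% |
| Distribution phase | +3 | 3.2 | 64% | 0.2 | 87% |
| Distribution phase | −3 | −3.0 | 63% | 0.1 | 87% |

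With 100 runs, the simulation error is about √(0.55 × 0.45/100) = 5 points on a 55% rate, and about 1.9/√100 = 0.2 ms on a mean.

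**A real effect hidden.** With a true 10 ms effect and −5 ms drift, the planned model returns 6.4 ms (single-phase, coverage 37%) or 4.6 ms (distribution phase, coverage 8%). With time and baseline added it returns 9.6 and 9.8 ms (coverage 88% and 87%).

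**Smaller drift.** A cosine of 3 to 5 ms from peak to trough, peaking 4 h after an 08:00 dose, gives 0.4 to 1.2 ms, with the lower 90% bound above zero in 6% to 10% of runs (nominal 5%). Spreading dosing over 6 h brings the bias to between −0.4 and +0.3 ms.

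**Predose rows.** If the Day 1 predose row is kept (change zero by construction), ±5 ms drift gives 5.5 to 6.9 ms in absolute size under the planned model, and the CI excludes zero in all 60 runs of each setting. Adding time and baseline then raises the spread of the estimates from 1.15–1.31 ms to 2.23–2.73 ms.

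**The case against.** The strongest reply is that the harm depends on a drift that neither document quantifies, and the smaller-drift runs show it can be minor. That stands: the omission can be read from the SAP, but its size is conditional.

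A reader might infer that time and concentration are fully aliased. They are not, because several dose levels give different concentrations at the same hour and a 39 h half-life makes the decline slow. A reader might also infer that the plan will produce a false QT signal. The documents do not support that either: the drift may be small, and it can bias the slope downward as well as upward.

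Nominal time is hours after dose, not clock time, and Protocol section 4 sets no clock time for dosing. It represents time of day only so far as dosing times are similar across subjects. In-clinic dosing on PK days (Protocol 4.7), with an 8 h sample to follow, makes similar times plausible but does not guarantee them.

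The analysis is exploratory, the code is a recommendation, Protocol 8.4.5 says the model may be fitted, no QT decision threshold is set, and Protocol 1.1.12 expects low QT risk. Tables of change by treatment and time point could reveal a drift shared by low and high doses. These facts limit the importance of the point. They do not correct the reported slope, and the SAP's adjustment guidance does not lead an analyst to a time term.

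**Conclusion.** The point holds as a conditional bias. With concentration as the only fixed effect, a common within-day QTcF change that moves with concentration is partly attributed to the drug. Under an assumed 3 to 5 ms change from predose, the planned model gives roughly 2 to 5 ms of spurious effect at the 4.5 mg exposure on post-dose rows, and its 90% CI excludes zero in about 25% to 95% of runs. With a smaller drift or widely spread dosing the bias is about 1 ms or less.

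These sizes rest on the assumed drift, variances and concentration profiles. They also treat the 24 h ECG, which the schedules list under Day 2, as part of the single-dose fit; leaving it out was not simulated.

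The missing time term is what matters. It might be inferred that omitting baseline QTcF also biases the slope, but nothing here shows that; baseline is a precision covariate of minor value. This is a cheap improvement to a secondary, exploratory analysis.

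**What to change.** In SAP 7.9, add nominal time after dose as a categorical fixed effect (CLASS and MODEL statements) and centred baseline QTcF as a second covariate, keeping the random intercept and slope. State that the Cycle 1 Day 1 fit uses post-dose rows only, and whether the 24 h reading belongs to it. SAP 8.3 says only that Day 1 predose concentrations are not imputed, which does not settle whether that row is fitted. Report the slope and 90% CI from this model, with the concentration-only fit as a sensitivity analysis.

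No new data are needed, and the code change is small. The price is a wider slope interval: about 0% to 20% on post-dose rows in simulation, and considerably more if predose zero rows are kept. The revised model's intervals covered 83% to 92% with no drug effect, using normal approximations, so the planned Kenward-Roger method should stay.

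### The fallback in SAP 7.9 permits a concentration-QTcF model with no subject term; if it were used while the intercept variance is not negligible, the 90% CI for the slope would be too narrow

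*SAP*

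**What the plan says.** The ECG summary in SAP 7.9 states: "Mixed effect model with random intercept and slope will be used to explore the relationship between the" change in QTcF and plasma concentration. The recommended PROC MIXED code has a MODEL statement ending in "concentration/solution cl alpha=0.10 ddfm=kenwardroger" and a RANDOM statement, "random intercept concentration/subject=usubjid type=un". There is no REPEATED statement, and the subject identifier is not a model effect.

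The guidance that follows has three parts. It remarks that the empirical option gives a more robust estimate. It advises starting with the unstructured matrix and then to "examine the covariance structure and adjust to reduce the number of parameters to be estimated, as needed". Finally, if the log contains the note "Estimated G matrix is not positive definite", it says that "the variances of the random intercepts or slopes may be so small that one or both should be replaced by fixed effects"; in the code this means taking those terms out of RANDOM. On output: "The point estimate and 90% confidence interval for the slope will be reported within the CSR text".

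The QT exposure-response effect is a secondary objective (Protocol 1.3.2, SAP 3.2). Protocol 8.4.5 makes the mixed model optional. The SAP, which states in Section 1 that it supersedes the protocol's statistical considerations, commits to the model at Cycle 1 Day 1 across schedules.

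**The concern.** The intercept and the concentration slope are already fixed effects in the MODEL statement. Removing both terms from the RANDOM statement therefore leaves ordinary least squares on repeated ECGs, with nothing in the code linking observations from one subject.

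Those observations are linked by construction. SAP 7.9 defines one baseline per subject and subtracts it from every post-dose value, so any error in the baseline is shared. Concentration also differs largely between subjects: Part 1 doses run from 0.75 to 4.5 mg (Protocol 1.4.4), and the 39-hour half-life (Protocol 1.1.5) implies a slow fall over 24 hours. When both the outcome and the covariate are positively correlated within subject, a regression that ignores the subject understates the standard error of the slope.

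The trigger is a poor guide to the remedy. A singular G matrix can come from a slope variance near zero, or from an intercept-slope correlation at its boundary, while the intercept variance remains substantial. At stake is whether an interval labelled 90% in the clinical study report covers at about that rate.

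**Working it through.** **Stated figure.** The code sets alpha = 0.10; 1 - 0.10 = 0.90, which agrees with the 90% CI to be reported. The documents give no QTc variance, sample size or power for this analysis, so nothing else can be reproduced.

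**Inputs from the documents.**
- Post-dose ECGs with matched PK in Cycle 1: 2, 4 and 8 h on Day 1, and 24 h on Day 2 (Protocol Tables 5.5.1-1 to 5.5.1-3), so m = 4.
- Subjects by dose over the three schedules (Protocol 1.4.4): 0.75 mg 5; 1.25 mg 4; 2 mg 13 + 4 + 6 = 23; 3 mg 10 + 4 + 12 = 26; 4.5 mg 12 + 11 = 23; total 81.
- Half-life 39 h (Protocol 1.1.5); AUC(INF) 4.102 µg·h/mL after 0.75 mg (Protocol 1.4.2).

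**Step 1: clustering formula.** True SE / naive SE = sqrt(1 + (m - 1) × rho_x × rho_y), where rho_x and rho_y are the within-subject correlations of concentration and of change in QTcF. Simulated concentrations for this dose mix give rho_x of about 0.80. The shared baseline alone gives rho_y = b / (b + s), with b and s the baseline and post-dose error variances: 0.25 if b = s/3, and 0.5 if b = s.
- rho_y = 0.25: sqrt(1 + 3 × 0.80 × 0.25) = sqrt(1.6) = 1.26; 1.645 / 1.26 gives coverage of about 81%.
- rho_y = 0.5: sqrt(1 + 3 × 0.80 × 0.5) = sqrt(2.2) = 1.48; coverage of about 73%.

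The direction is not universal. With rho_x = 0 the naive interval is correct. With rho_x = -0.33 and rho_y = 0.5 it is too wide (98%).

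**Step 2: simulation, 600 trials per setting.** Assumed, not in the documents: residual SD 7 ms; intercept and slope SDs as tabulated (slope SD in ms per SD of concentration); one-compartment PK with ka 1/h and CVs of 25-50%. Intervals use t quantiles, not Kenward-Roger. The table is limited to trials with a singular estimated G, which stands in for the SAS note.

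| Setting | Trials with singular G | Median intercept variance (ms²) | Coverage, both dropped | Coverage, intercept kept |
|---|---|---|---|---|
| 81 subjects, intercept SD 6, slope SD 0 | 61% | 35.3 | 67% | 86% |
| 81 subjects, intercept SD 4, slope SD 0 | 58% | 15.7 | 79% | 89% |
| 81 subjects, intercept SD 6, slope SD 1.5 | 45% | 44.5 | 71% | 86% |
| 20 subjects at one dose, intercept SD 6, slope SD 0 | 66% | 32.7 | 80% | 90% |
| 81 subjects, intercept SD 0.5, slope SD 0 | 90% | 0.0 | 89% | 90% |

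In the first four rows the note appears while the intercept variance is clearly not near zero. Median interval width with both terms dropped against intercept kept was 1.68 against 2.12 (intercept SD 6, slope SD 0) and 1.47 against 1.79 (intercept SD 4), in ms per SD of concentration. In the last row dropping both is harmless.

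**Step 3: a separate simulation with both terms dropped in every trial.** No true drug effect, total SD 10 ms and an assumed declining PK profile. Rejection at nominal 10% was 18% at within-subject correlation 0.3, about 23-25% at 0.5 and 29% at 0.7, but 11-12% at 0.05. Using only the three Day 1 times hardly matters: 23.9% against 24.5% at correlation 0.5.

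**Step 4: the same set-up, with the analyst checking G.** When G is singular, the slope is dropped, and the intercept only if its estimated variance is below 1 ms². Over 150 trials per setting G was singular in 51-53%. Both terms were dropped in 0 of 150 at correlation 0.3 and 0 of 150 at 0.5, and rejection was 7-9%. With 150 trials the Monte Carlo SE is sqrt(0.1 × 0.9 / 150) = 2.4 points, so this is compatible with 10%.

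**The case against.** The strongest reply is that the SAP does not tell the analyst to drop both terms whenever the note appears. It ties dropping to variances that may be very small, it allows one term as well as both, and the preceding advice to simplify the covariance structure already permits removing the intercept-slope covariance. An analyst who looks at the fitted matrix would usually drop only the slope, and Step 4 shows that this stays near nominal. This stands. A reader might infer that the 18-29% rejection rates are the error rate of the plan; they are not, because they assume both terms are dropped in every trial regardless of the estimates.

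The reply goes on that the model is exploratory, the code is only recommended, the study has no formal hypothesis, and QT safety is also covered by categorical tables, summary statistics, plots and listings that do not use this model. This stands too. A reader might infer that a narrow interval would lead the trial to declare or rule out a QT effect, but no decision rule is attached to the slope.

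The empirical option is a weaker defence. It is a remark that is absent from the recommended code, and once both terms leave the RANDOM statement no subject is named for it to cluster on.

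What the reply does not remove is that the text expressly allows both terms to go, with no check, order or floor.

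**Conclusion.** The point holds as a gap in the fallback rule. SAP 7.9 permits, on a message that does not identify which variance is small, a model that treats a subject's ECGs as independent. If that branch were taken with an intercept SD of 4-6 ms against a residual SD of 7 ms, the nominal 90% interval would cover about 67-80% of the time. Keeping the intercept in the same trials gives 86-90%. With an intercept SD of 0.5 ms, dropping both costs essentially nothing.

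These figures are a worst case. They rest on assumed SDs, an assumed PK profile and the analyst choosing to drop both terms. The direction rests on features the documents do give: the dose range, the long half-life and the shared baseline. The documents do not support reading this as a planned invalid analysis or as a threat to the primary safety objective. It concerns one descriptive estimate for a secondary objective, and is worth correcting because the correction is so cheap.

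**What to change.** In the SAP 7.9 guidance after the code, delete the words *or both* and replace the fallback with an ordered rule:

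1. If G is not positive definite, first remove the intercept-slope covariance (for example `type=vc`).
2. If the problem remains, remove the random slope.
3. Always keep `random intercept / subject=usubjid`, or an equivalent `repeated / subject=usubjid type=cs`, as the minimum model.

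The cost is one sentence of SAP text and one line of code, with no change to data collection or sample size. Where the intercept variance is material the interval will be wider than with both terms dropped (2.12 against 1.68 in the first simulated setting); that extra width reflects the clustering.
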